I confirm that I have read this protocol, I understand it, and I will work according to this protocol and to the ethical principles stated in the latest version of the Declaration of Helsinki, the applicable ICH guidelines for good clinical practices, and the applicable federal, state, and local laws, rules, and regulations relating to the conduct of the protocol. I have read and understand the information in the Investigators' Brochure (or Manufacturer's Brochure) regarding the risks and potential benefits. I will promptly submit the protocol to the applicable IRB for review and approval. Once the protocol has been approved by the IRB, I understand that any modification made during the course of the study must first be approved by the IRB, prior to implementation except when such modification is made to remove an immediate hazard to the subject. I certify that I, and the study staff, have received the requisite training to conduct this research protocol. I agree to maintain adequate and accurate records in accordance with Columbia University and Herbert Irving Comprehensive Cancer Center policies, Federal, state and local laws and regulations. I agree to maintain the confidentiality of all information received or developed in connection with this protocol.

Signature of Principal Investigator

Date

Principal Investigator Name (Print)

[figure not shown]
Name of Institution

Protocol Synopsis

Title	A phase II trial of atezolizumab + carboplatin + etoposide with liver-directed radiotherapy in extensive stage small cell lung cancer (ES-SCLC) patients with liver metastases
Short Title	Atezo+chemo+RT in ES-SCLC with liver metastases
Protocol Number	AAAT0174
Phase	Phase II
Methodology	Single arm, open label study
Study Duration	36 months
Study Center(s)	Multicenter, projected 3 centers in total
Objectives	To assess the efficacy of liver-directed SBRT added to standard of care first line chemoimmunotherapy as measured by the 6 month progression free survival rate in ES-SCLC patients with liver metastases
Number of Subjects	18 patients
Diagnosis and Main Inclusion Criteria	Previously untreated ES-SCLC with measurable liver metastases
Study Product, Dose, Route, Regimen	Carboplatin AUC 5 mg/ml/min IV, Day 1, q21 days x4 cycles Etoposide 100 mg/m ² IV, Days 1-3, q21 days x 4 cycles Atezolizumab 1200 mg IV, Day 1, q21 days until disease progression SBRT within +/-3 days of cycle 2, 10 Gy 3 doses on alternating days
Duration of administration	Four 21-day cycles of atezolizumab+chemotherapy followed by atezolizumab maintenance until progression
Reference therapy	Atezolizumab + carboplatin+ etoposide
Statistical Methodology	A total of 16 evaluable patients are needed to detect an increase in 6 month PFS from 20% (historical control) to 45%. This estimate was based on one-sided exact binomial test, with a type I error of 0.10 and power of 0.80. To account for a 10% dropout rate, 18 patients will be accrued to the study. The remainder of the analysis is exploratory.

**Columbia University Irving Medical Center
Herbert Irving Comprehensive Cancer Center
CUMC IRB – AAAT0174**

Protocol Schema:

Contents

Protocol Signature Page	3
1 Introduction	10
2 Study Objectives	10
2.1 Primary Objective	10
2.2 Secondary Objective	10
3 Background	11
4 Investigational Agents	16
4.1 Atezolizumab	16
4.1.1 Preclinical Data	16
4.1.2 Clinical Pharmacokinetics and Immunogenicity	17
4.1.3 Clinical Data to Date	18
4.1.4 Safety Data to Date	18
4.2 Other Agent(s)	20
4.3 Radiation	20
5 Study Design	20
5.1 General Design	20
5.2 Intervention	21
5.3 Specimen Collection and Processing	21
6 Subject Selection and Withdrawal	22
6.1 Inclusion Criteria	22
6.2 Exclusion Criteria	24
6.3 Inclusion of Women and Minorities	27
6.4 Subject Recruitment	27
6.5 Early Withdrawal of Subjects	27
6.5.1 When and How to Withdraw Subjects	27
6.5.2 Treatment Beyond Radiographic Progression	27
6.5.3 Data Collection and Follow-up for Withdrawn Subjects	28
7 REGISTRATION PROCEDURES	28
CUIMC Research Participant Registration	28
8 TREATMENT PLAN	30

**Columbia University Irving Medical Center
Herbert Irving Comprehensive Cancer Center
CUMC IRB – AAAT0174**

8.1	Agent Administration	30
8.2	Radiation Therapy	30
8.3	General Concomitant Medication and Supportive Care Guidelines	30
8.4	Duration of Therapy	32
8.5	Duration of Follow Up	32
8.6	Criteria for Removal from Study	32
9	DOSING DELAYS/DOSE MODIFICATIONS	32
9.1	General Notes Regarding Dose Modification	33
9.2	Atezolizumab Dose Modification	33
9.3	Carboplatin Dose Modification	34
9.3.1	Hematologic toxicity	34
9.3.2	Non-hematologic toxicity	35
9.3.3	Other toxicity	36
9.4	Etoposide Dose Modification	36
9.5	Potential Overlapping Toxicities	36
10	ADVERSE EVENTS: LIST AND REPORTING REQUIREMENTS	37
10.1	Safety Parameters and Definitions	37
10.2	Definitions	37
10.3	Recording of Adverse Events	41
10.3.1	Assessment of Adverse Event	41
10.3.2	Assessment of Severity of Adverse Events	42

1 INTRODUCTION

This document is a protocol for a human research study. This study is to be conducted according to US and international standards of Good Clinical Practice (FDA Title 21 part 312 and International Conference on Harmonization guidelines), applicable government regulations and Columbia University Irving Medical Center institutional research policies and procedures.

The standard of care first-line treatment for extensive stage SCLC is atezolizumab with platinum-etoposide, based on the IMpower133 study. In this study, the overall survival benefit with atezolizumab was 16.8 vs. 11.2 months in patients without liver metastases (63% of patients) but only 9.3 vs. 7.8 months in patients with liver metastases (37% of patients)¹. These data and retrospective studies highlight that liver metastases are a negative prognostic factor in SCLC². Additionally, the IMpower133 results suggest that liver involvement is associated with resistance to immune checkpoint inhibitors (ICI) in SCLC, an observation also seen in metastatic melanoma and non-small cell lung cancer³. It is hypothesized that liver-mediated tolerance mechanisms may induce systemic immune suppression that contributes to ICI resistance^{4,5}. Using radiation therapy (RT) in this context may be a viable approach to overcoming resistance. Apart from direct cytotoxic effects, RT promotes tumor-specific immunity through several mechanisms. Radiation upregulates MHC-I expression on tumor cells and generates tumor neoantigens that promote immune surveillance. RT also stimulates the release of damage associated molecular patterns (DAMPs) after immunogenic cell death that promote effective T cell priming^{6,7}. Preclinical studies suggest that RT can act synergistically with ICI to enhance the anti-tumor response⁸. Early clinical data also suggest that the combination of RT with ICI can promote a strong and durable anti-tumor response within and beyond the boundaries of the radiation target⁹⁻¹¹. We therefore propose a phase II trial adding stereotactic body radiation therapy (SBRT), directed at liver metastases, to standard of care treatment atezolizumab+chemotherapy in SCLC. We hypothesize that this combination will lead to improved local control and progression free survival in ES-SCLC with liver involvement, and provide key insights into the mechanisms of immune response/evasion.

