2 STUDY OBJECTIVES

21 Primary Objective

- To assess the efficacy of liver-directed SBRT when added to standard of care atezolizumab+chemotherapy as measured by the progression free survival rate at 6 months

22 Secondary Objective

- To assess the efficacy of adding liver-directed SBRT as measured by overall survival, progression-free survival, and the overall response rate
- To evaluate the feasibility and safety of adding liver-directed SBRT to standard of care atezolizumab+chemotherapy
- To describe the rate of in-field local control and out of field disease progression.

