The trials of combination immunotherapy with RT in ES-SCLC are still in early phases and mostly ongoing. In a phase I trial, patients with ES-SCLC who completed induction chemotherapy received 45 Gy of thoracic RT in 15 daily fractions along with pembrolizumab every 3 weeks for up to 16 cycles in a 3+3 dose escalation design. Thirty-three patients completed treatment per protocol with no dose limiting toxicities and few high-grade adverse events. Notably the trial enrolled patients regardless of their response to induction chemotherapy and PD-L1 status. The reported median PFS was 6.1 months and OS was 8.4 months compared to historical results of 4 months PFS and 8 months OS with thoracic RT alone in chemotherapy responders in a phase III trial^{17,37}. Although the clinical benefits are not clear from this trial, a larger study with a homogeneous population is necessary to assess relative efficacy. Several ongoing trials are also evaluating the combination of thoracic RT with anti-CTLA4 and/or anti-PD-1 after induction chemotherapy (NCT03923270, NCT03043599). Additionally there are a few studies under way of immunotherapy with RT in the second line setting (NCT02701400, NCT03262454). Of note, in all of these trials RT has been targeted at thoracic lesions. To our knowledge, no trials with RT targeting metastatic lesions in combination with ICI have been previously done.

Stereotactic radiation therapy for liver metastases

Stereotactic radiation therapy for liver lesions has been well described for both primary hepatocellular carcinoma and metastatic disease³⁸⁻⁴⁰. In a large multi-institutional retrospective series of 427 patients with 568 liver metastatic lesions (from various histologies) treated with SBRT, local control (LC) of the treated lesions was durable. Median duration of local control was 51 months. Small tumors (< 40 cm³) were noted to have improved median local control rates of 52 months, compared to 39 months for tumor volumes \geq 40 cm³. No grade 3 or higher toxicity was reported. The selected dose/fractionation of 30 Gy in 3 fractions in the study has also been shown to be well tolerated⁴⁰. In a phase I dose-escalation study of SBRT for liver metastases, the 30 Gy in 3 fraction regimen shows no grade 3 or higher toxicity⁴¹. This regimen is also an accepted treatment dose for the current SABR-COMET-10 phase III trial analyzing the effect of ablative SBRT in patients with oligometastatic disease⁴².

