Target lesions: All measurable lesions up to a maximum of 2 lesions per organ and 5 lesions in total, representative of all involved organs, should be identified as target lesions and recorded and measured at baseline. The liver lesions that undergo SBRT will be excluded from the target lesions. Target lesions should be selected on the basis of their size (lesions with the longest diameter), be representative of all involved organs, but in addition should be those that lend themselves to reproducible repeated measurements. It may be the case that, on occasion, the largest lesion does not lend itself to reproducible measurement in which circumstance the next largest lesion which can be measured reproducibly should be selected. A sum of the diameters (longest for non-nodal lesions, short axis for nodal lesions) for all target lesions will be calculated and reported as the baseline sum diameters. If lymph nodes are to be included in the sum, then only the short axis is added into the sum. The baseline sum diameters will be used as reference to further characterize any objective tumor regression in the measurable dimension of the disease.

Non-target lesions: All other lesions (or sites of disease) including any measurable lesions over and above the 5 target lesions should be identified as non-target lesions and should also be recorded at baseline. Measurements of these lesions are not required, but the presence, absence, or in rare cases unequivocal progression of each should be noted throughout follow-up.

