13.5.2 Evaluation of Non-Target Lesions

Complete Response (CR): Disappearance of all non-target lesions. All lymph nodes must be non-pathological in size (<10 mm short axis).

Non-CR/Non-PD: Persistence of one or more non-target lesion(s).

Progressive Disease (PD): Appearance of one or more new lesions and/or unequivocal progression of existing non-target lesions. Unequivocal progression should not normally trump target lesion status. It must be representative of overall disease status change, not a single lesion increase. Although a clear progression of “non-target” lesions only is exceptional, the opinion of the treating physician should prevail in such circumstances, and the progression status should be confirmed at a later time by the review panel (or Principal Investigator).

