13.5.3 Evaluation of Disease Control Relative to the Radiation Field

In-field local control will be assessed in patients with at least 6 months of follow-up imaging post-SBRT. Follow-up images will be compared (by using image fusion software) with the SBRT treatment plan to evaluate local control (LC).

In-field local progression: Defined as new or progression lesions that develop within or at the margin of the radiation planning target volume (PTV)

Out-of-field progression: Defined as the development of lesions outside the PTV as assessed by RECIST v1.1. criteria.

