- In-field local control will be defined as the absence of disease progression within the planning target volume (PTV) as per RECIST v1.1 on CT at 6 months following radiation treatment
- Out of field disease progression will be defined as the development of lesions outside the PTV as assessed by RECIST v1.1 criteria at 6 months following radiation treatment

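### Sections 15.1 and 13.5.3 define in-field local control differently, and neither gives a usable growth criterion for an irradiated lesion

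*Combined protocol and SAP*

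**What the plan says.** The Introduction names local control as one of two expected clinical gains: "We hypothesize that this combination will lead to improved local control and progression free survival in ES-SCLC with liver involvement". Section 2 makes it a secondary objective, worded descriptively: "To describe the rate of in-field local control and out of field disease progression". Section 15.2 reports the rate with a 95% confidence interval and no test or comparator.

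Two sections define the endpoint.

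- Section 15.1: "In-field local control will be defined as the absence of disease progression within the planning target volume (PTV) as per RECIST v1.1 on CT", assessed 6 months after radiation.
- Section 13.5.3: "In-field local control will be assessed in patients with at least 6 months of follow-up imaging post-SBRT". Follow-up scans are fused with the SBRT plan, and in-field progression means new or progressing lesions inside the PTV or on its edge.

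Three other places decide what RECIST means for these lesions.

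- Section 13.3, target lesions: "The liver lesions that undergo SBRT will be excluded from the target lesions".
- Section 13.3, non-target lesions: every lesion that is not a target is non-target, and "Measurements of these lesions are not required". The same sentence does ask that presence, absence or, rarely, unequivocal progression of each lesion be noted.
- Section 13.5.2, on unequivocal progression of non-target lesions: "It must be representative of overall disease status change, not a single lesion increase". In exceptional cases the treating physician's opinion prevails, subject to later confirmation.

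The only numeric progression rule, at least 20% and at least 5 mm, is in Section 13.5.1 and applies to the sum of target-lesion diameters. Section 8.2 allows up to three lesions to be irradiated.

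**The concern.** Section 15.1 relies on a criterion that does not fit the lesions it is meant to judge. An irradiated lesion cannot enter the target sum, so the 20% and 5 mm rule never reaches it. What remains is the non-target rule, which looks at overall disease status and normally discounts growth of one lesion. In-field control, however, is a question about individual lesions.

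Section 13.5.3 asks the right question but does not say how much growth is progression, or against which scan growth is judged. Two centers could classify the same scan differently, each with text to support it. Because diameters of irradiated lesions need not be recorded, the data needed to settle a disagreement may not be in the database. Old scans could be remeasured, but a threshold chosen after outcomes are known is not prespecified.

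Neither section says whether the rate counts patients or lesions, although one patient may contribute up to three.

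At stake is whether the reported local-control rate, which describes the direct effect of the added treatment, can be interpreted.

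**Working it through.** **1. The plan's own figures.** No local-control rate, target or sample size is stated, so there is nothing to reproduce for this endpoint. The primary design in Section 15.1 was checked to confirm that it stands apart. With 16 patients, success at 6 or more, p0 = 0.20 and p1 = 0.45:

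- P(X ≥ 6 | 16, 0.20) = 0.0817, within the one-sided 0.10.
- P(X ≥ 6 | 16, 0.45) = 0.8024, meeting 80%.
- In a search over n = 8 to 21, 16 is the smallest n that meets both limits.
- 16 / 0.90 = 17.8, rounded up to 18.

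None of these uses local control.

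**2. One lesion under both definitions.** Take an irradiated lesion with a nadir of 30 mm that grows to 45 mm while all other disease is stable.

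| Rule | Does it apply? | Result |
|---|---|---|
| 13.5.1, 20% and 5 mm | No; SBRT lesions are outside the target sum | No progression |
| 13.5.2, non-target | Yes, by default category | Not normally progression; physician may override |
| 15.1, RECIST within the PTV | Inherits the two rows above | Can be read as controlled |
| 13.5.3, progressing lesion in the PTV | Yes | On its face progression, but no threshold or reference scan |

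The growth is 15 mm, or 15/30 = 50%, so this is not a borderline case. The two definitions can still give opposite answers.

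**3. Effect of one misread patient.** If one patient with a regrown lesion is counted as controlled, the rate rises by 1/n. The plan gives no n for this endpoint, so the values below are assumptions. The first is the 16 evaluable patients. The others assume that mainly progression-free patients have 6 months of imaging after SBRT: 0.45 × 16 = 7.2 and 0.20 × 16 = 3.2. Intervals are exact 95%.

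| Assumed n | One failure recognized | Same failure missed | Shift |
|---|---|---|---|
| 16 | 15/16 = 93.8% (69.8 to 99.8) | 16/16 = 100% (79.4 to 100) | 6.25 points |
| 7 | 6/7 = 85.7% (42.1 to 99.6) | 7/7 = 100% (59.0 to 100) | 14.3 points |
| 3 | 2/3 = 66.7% (9.4 to 99.2) | 3/3 = 100% (29.2 to 100) | 33.3 points |

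**4. What a lesion-level rule would do.** Requiring at least 20% and at least 5 mm from the lesion's own nadir d sets failure at max(1.2d, d + 5). For nadirs of 10, 25, 30 and 50 mm this is 15, 30, 36 and 60 mm. The lesion in step 2 would fail clearly.

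**The case against.** The best defense is that Section 13.5.3 already provides a dedicated method at the level of the PTV, and that a sensible reader would use it. The single-lesion sentence in Section 13.5.2 is written for overall disease status, so carrying it into a PTV-restricted endpoint is one reading and not something the text states. That section also lets physician judgement prevail, and Section 13.3 asks for unequivocal progression of each lesion to be noted. The endpoint is descriptive, with no decision attached.

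Most of this stands, and it limits the point. It does not remove it: 15.1 names RECIST and does not refer to 13.5.3, and 13.5.3 does not say what progression is. Image fusion locates a lesion relative to the PTV but does not say how much growth is failure. Physician judgement in an open-label trial projected at three centers does not replace a criterion.

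Two stronger readings are tempting and not supported.

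- A reader might infer that the reported rate will be close to 100% whatever SBRT achieves. New in-field lesions still count as failures under 13.5.3, and the physician exception remains, so the documents do not force that result.
- A reader might infer that the endpoint is fixed per patient and so cannot be compared with the 427-patient, 568-lesion series in Section 3. That series is described with the words "local control (LC) of the treated lesions was durable", but only as background. No section fixes a per-patient unit or plans such a comparison. Turning its median control times into 6-month rates for this trial would need exponential failure, independent lesions and failures consisting only of isolated regrowth, none of which the documents state.

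**Conclusion.** The point holds as a conflict between two definitions with no usable lesion-level criterion in either. As written, an isolated regrowing SBRT lesion can be counted as controlled under 15.1 and as in-field progression under 13.5.3.

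The reach is limited. It affects one descriptive secondary endpoint with no formal test, and each misread patient shifts the rate by 1/n: 6.25 points at an assumed 16 patients and 14.3 at an assumed 7. How many patients would be misread cannot be derived from the documents. The sample size, the 6-of-16 rule and the error rates for 6-month PFS are unaffected. The change should be made, but the trial's main conclusion does not depend on it.

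**What to change.** 1. In Section 15.1, replace the RECIST reference for in-field control with a pointer to Section 13.5.3.
2. In Section 13.5.3, require the longest diameter of each irradiated lesion (at most three) at baseline and at every scheduled scan, kept outside the target sum.
3. Define in-field failure as growth of that lesion by at least 20% and at least 5 mm from its own nadir, or a new lesion in or at the edge of the PTV. The two thresholds are those already in Section 13.5.1.
4. State the unit of analysis. Report per-lesion counts, and a per-patient rate with an exact 95% confidence interval.
5. Say whether in-field failure alone is a PFS event, so that the new rule does not silently alter RECIST progression.

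The cost is protocol and case report form wording, and up to three extra diameters on CT scans already planned. The main drawback is that swelling after SBRT may mimic growth. Failures not confirmed on a later scan should be flagged where such a scan exists. Confirmation should not be mandatory, because under Section 5.2 assessments end at RECIST progression unless treatment continues, so a later scan may not be available.

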2 STUDY OBJECTIVES

21 Primary Objective

- To assess the efficacy of liver-directed SBRT when added to standard of care atezolizumab+chemotherapy as measured by the progression free survival rate at 6 months

22 Secondary Objective

- To assess the efficacy of adding liver-directed SBRT as measured by overall survival, progression-free survival, and the overall response rate
- To evaluate the feasibility and safety of adding liver-directed SBRT to standard of care atezolizumab+chemotherapy
- To describe the rate of in-field local control and out of field disease progression.

3 BACKGROUND

SCLC Background

SCLC accounts for approximately 15% of new cases of lung cancer, and is responsible for an estimated 250,000 annual deaths worldwide. Smoking is the strongest risk factor for SCLC development and the institution of smoking cessation programs has led to decreasing incidence.¹² Nevertheless, treatment options are limited and survival remains poor. SCLC is characterized by rapid tumor growth, earlier development of distant metastases and a high degree of genomic instability. Extensive stage (ES) disease is typically very sensitive to upfront chemotherapy with initial response rates of 60-65% but the disease rapidly recurs leading to median overall survival estimates historically under 10 months^{13,14}. For decades the only therapeutic modalities with demonstrated clinical benefit were platinum-based chemotherapy and radiation, although in recent years there have been promising developments incorporating the use of immunotherapy and targeted agents.

The phase III IMpower133 trial introduced a new standard of care for the first-line treatment of ES-SCLC. Newly diagnosed ES-SCLC patients were randomly assigned to receive carboplatin+etoposide with either atezolizumab or placebo for four 21-day cycles followed by atezolizumab or placebo. Median overall survival (OS) was 12.3 months with atezolizumab vs 10.3 months in the placebo group (p=0.007). PFS was longer, at 5.2 months, with atezolizumab versus 4.3 months with chemotherapy alone.¹ Based on these results the FDA approved atezolizumab in the first line setting in March 2019. Similarly, the addition of durvalumab to platinum based chemotherapy was associated with a 27% improvement in overall survival in the CASPIAN trial, which led to recent FDA approval in March 2020¹⁵.

Thoracic radiation and/or prophylactic cranial radiation can also be included in first-line treatment of ES-SCLC. Consolidative thoracic RT may be considered in patients with complete response to initial systemic therapy or those with low-bulk disease. Jeremic et al demonstrated that accelerated hyperfractionated RT as consolidative treatment was associated with an improved median survival of 17 vs 11 months.¹⁶ The Dutch CREST trial showed an improvement in 2-year but not 1-year survival with consolidative RT.¹⁷ Notably thoracic RT can potentially add significant toxicity depending on the radiation regimen. The role of thoracic RT is under investigation in the chemoimmunotherapy era.

Prophylactic cranial radiation (PCI) is a controversial treatment modality in ES-SCLC, explored due to high rates of brain metastases. In the rare patients who achieve a complete response to chemotherapy, a meta-analysis showed that PCI was associated with a 5.4% survival benefit at 3 years¹⁸. Additionally, in a randomized trial of PCI vs observation in ES-SCLC patients who had any response to chemotherapy, the PCI arm had reduced incidence of symptomatic brain metastases at one year with improved 1 year OS (27.1% vs 13.3%)¹⁹. However, this study did not standardize the radiation dose and did not require brain imaging prior to PCI, which may have skewed the results. A subsequent Japanese study found no difference in the OS of patients who received PCI and all patients had a brain MRI prior to radiation.²⁰ Therefore, PCI or close brain

surveillance imaging are considered acceptable options per the NCCN guidelines, but more definitively beneficial treatments are needed.

Rationale for targeting patients with liver metastases

Several studies have highlighted that liver metastases are a negative prognostic factor in SCLC. In an analysis of 6459 patients with SCLC with metastatic disease from the Surveillance, Epidemiology, and End Results (SEER) database collected between 2010 and 2012, the incidence of liver metastases was 61.9%, and in one third of patients the liver was the only site of metastatic disease. SCLC with liver metastases had a reduced median OS of 4 months compared to 6 months among patients with other metastases ($p=0.017$)²¹. Other retrospective studies also demonstrated poor outcomes for patients with liver metastases, including worse response to chemotherapy^{22,23}.

A proposed mechanism for worse survival outcomes among patients with liver involvement is that the liver is an immunosuppressive organ with impaired immune surveillance of intrahepatic metastases². This hypothesis may also account for poor response to immunotherapy seen in patients with liver metastases. In the aforementioned IMpower133 study, patients without liver metastases (63% of patients) who received atezolizumab with chemotherapy had an OS of 16.8 months versus 11.2 months in those who received chemotherapy alone. In the 37% of patients who had liver metastases, however, OS was 9.3 months with atezolizumab versus 7.8 months with chemotherapy alone (HR 0.81, 95% CI 0.55-1.20). A similar effect was seen on PFS where patients with liver metastases had no significant benefit from the addition of atezolizumab (4.3 months with atezolizumab vs. 4.2 months with placebo)¹. These results suggest that not only are liver metastases a poor prognostic factor in SCLC, but they also associate with immunotherapy resistance.

The resistance to immune checkpoint inhibitors seen in SCLC with liver metastases has also been observed in other cancer types including non-small cell lung cancer (NSCLC) and melanoma. Tumeh et al. assessed the response to pembrolizumab in several cohorts of patients treated under the Keynote 001, 002, and 006 trials. Presence of liver metastases was an independent predictive marker of reduced PFS among melanoma patients in a multivariable analysis (odds ratio of PFS 1.85, 95% CI 1.37-2.50, $p<0.0001$). Among 223 patients with melanoma, those with liver metastases had a PFS of 5.1 months compared to 20.1 months for patients without liver metastases ($p=0.001$). Similarly, among 165 patients with NSCLC who were treated with pembrolizumab, including 46 with liver metastases, PFS was significantly reduced in the liver metastases group (1.28 months vs 4.03 months, $p=0.0094$).³ In this and other retrospective studies in NSCLC, worse clinical outcomes in patients with liver metastases were observed irrespective of PD-L1 status²⁴.

The degree of tumor CD8+ T cell infiltration at the invasive margin has previously been shown to correlate with response to immunotherapy in melanoma. Tumeh et al. also used pre-treatment tumor samples from melanoma patients who participated in the Keynote trials to show that the subset of patients with liver metastases had depleted marginating CD8+ T cells in their distant and cutaneous metastases³. A separate group showed that melanoma patients with liver

metastases had a lower CD8/Foxp3+ T reg ratio and a decreased percentage of activated PD-1+/CTLA-4+ CD8 cells in the immune infiltrates of the distant primary tumor.⁴ These findings suggest that the presence of liver metastases has an immunosuppressive effect beyond the liver. However, the systemic impact of liver metastases on antitumor immunity is not well understood.

Preclinical rationale for combining radiation with immunotherapy

Using radiation in combination with immunotherapy may be a promising approach to overcome immunotherapy resistance in patients with liver metastases. Tumor cells evolve to avoid recognition and destruction by the immune system through several escape mechanisms including downregulation of MHC class I expression, upregulation of inhibitory cytokines, and increased infiltration of the tumor by immunosuppressive cells. Beyond its cytotoxic effects through lethal DNA damage, radiation may convert the tumor immune microenvironment into an immune activated state.

Evidence of immunomodulation via radiation therapy (RT) includes upregulation of MHC class I expression on tumor cells in a dose-dependent manner after RT exposure²⁵. RT also results in increased peptide production, including formation of novel proteins, and enhanced antigen presentation to primed CD8+ T cells, augmenting the anti-tumor response. Additionally, RT promotes the release of inflammatory cytokines and chemokines by stressed tumor and stromal cells that attract immune effector cells into the tumor microenvironment. This includes the upregulation of interferon by infiltrating myeloid cells, which augments the cross-priming capacity of dendritic cells to expand antigen specific T cells and produce T cell dependent tumor regression²⁶. Furthermore, local irradiation promotes increased infiltration and retention of tumor antigen-reactive CD8+ T cells²⁷. Notably, in mouse models, CD8+ T cell depletion largely diminishes the therapeutic effect of RT²⁸. Together the aforementioned mechanisms may augment the immune system's anti-tumor response and contribute to the abscopal effect, a rare phenomenon, where radiation induces metastatic tumor regression at unirradiated sites.

Despite the adaptive immune response that may be triggered by radiation, tumors can also develop resistance mechanisms to escape immune mediated destruction. One mechanism is through the inhibition of T cell function by upregulation of PD-L1 on tumor cells after irradiation through interferon γ mediated signaling²⁹. Based on this finding Deng et al. administered anti-PD-L1 blockade with high dose ionizing irradiation (IR) and demonstrated enhanced tumor regression in an animal model. Additionally they found evidence of the abscopal effect in their model. In evaluating the immunomodulating effects of combination treatment, they showed that it enhanced tumor antigen-specific T cell function locally and systemically and decreased inhibitory myeloid-derived suppressor cells (MDSCs) within the tumor microenvironment⁸. Other groups have also provided evidence to support the use of combination PD-L1 or CTLA-4 blockade with radiation in enhancing the anti-tumor response in animal models²⁹⁻³¹.

Clinical rationale for combining radiation with immunotherapy

**Columbia University Irving Medical Center
Herbert Irving Comprehensive Cancer Center
CUMC IRB – AAAT0174**

Although the clinical evidence for the combination of radiation therapy and immunotherapy is more limited, numerous case reports, retrospective studies, early stage trials, and ongoing prospective trials highlight the potential for this approach in augmenting the anti-tumor response.

Several phase I trials suggested the safety of combining ipilimumab with radiation in the treatment of solid malignancies. However the efficacy of anti-CTLA-4 blockade with hypofractionated radiation was not robust with clinical benefit defined as partial response or stable disease outside of the radiation field seen in 23-36% of patients³¹⁻³³. In a prospective trial of 22 stage IV melanoma patients 50% of patients had a clinical benefit, including 27% who achieved an ongoing complete response³². In these trials the combination therapy was generally well tolerated. Clinical benefit was associated with increased markers of T cell reinvigoration and expansion of CD8+ T cells³³. The increased expression of PD-L1 with this treatment suggests a role for adding anti- PD-1/PD-L1 targeted treatment³¹.

Notably, in one study, liver irradiation produced increased proportions of T cells expressing ICOS, GITR, and 4-1BB, that are associated with proimmune activity. However, it also increased the proportion of cells expressing LAG3, TIM3, and PD1, which promote immune inhibition. This finding suggests that hepatic irradiation supports early systemic immune activation with compensatory mechanisms of increasing inhibitory antigen expression³³.

The clinical data regarding anti PD-1/PD-L1 blockade in combination with RT is more limited. In completed and ongoing trials a variety of schedules for immunotherapy and radiation administration have been adopted but the optimal timing and dosage for RT has not been established. In NSCLC, the PACIFIC trial randomized 713 patients with unresectable NSCLC to chemoradiation followed by adjuvant treatment with durvalumab, an anti-PD-L1 agent, or placebo. It demonstrated a significantly prolonged PFS of 16.8 months for the durvalumab patients compared to 5.6 months for those who received placebo³⁴.

However other studies suggest the superior efficacy of concurrent RT with immunotherapy. Despite inherent limitations of the study design, in a retrospective study of 758 patients who received immunotherapy and radiation, concurrent ICB with RT and hypofractionated RT was associated with improved OS³⁵. In a recent phase I trial, 21 patients with stage III NSCLC received pembrolizumab, an anti-PD-1 agent, concurrently with chemoradiation in a 3+3 design. The 12 month PFS was 69.7% in this trial compared to 55.7% seen in the PACIFIC study. Of note, both trials had elevated rates of pneumonitis, including 33% of patients with at least grade 2 pneumonitis in the phase I trial^{34,36}. A phase II study of concurrent chemoradiation with pembrolizumab is underway. A signal for synergy between radiation and anti-PD-1 was also seen in the metastatic NSCLC setting in a phase II trial of pembrolizumab with stereotactic body RT (SBRT) on a single tumor site. In this study, the overall response rate was 36% at 12 weeks with combination treatment compared to 18% with pembrolizumab alone. However the trial did not meet its prespecified end point critiera of 50% ORR at 12 weeks for the combination treatment group¹⁰. In the oligometastatic disease setting, a single-arm phase II study investigating pembrolizumab following local ablative therapy revealed improved PFS compared to historical controls⁹.

The trials of combination immunotherapy with RT in ES-SCLC are still in early phases and mostly ongoing. In a phase I trial, patients with ES-SCLC who completed induction chemotherapy received 45 Gy of thoracic RT in 15 daily fractions along with pembrolizumab every 3 weeks for up to 16 cycles in a 3+3 dose escalation design. Thirty-three patients completed treatment per protocol with no dose limiting toxicities and few high-grade adverse events. Notably the trial enrolled patients regardless of their response to induction chemotherapy and PD-L1 status. The reported median PFS was 6.1 months and OS was 8.4 months compared to historical results of 4 months PFS and 8 months OS with thoracic RT alone in chemotherapy responders in a phase III trial^{17,37}. Although the clinical benefits are not clear from this trial, a larger study with a homogeneous population is necessary to assess relative efficacy. Several ongoing trials are also evaluating the combination of thoracic RT with anti-CTLA4 and/or anti-PD-1 after induction chemotherapy (NCT03923270, NCT03043599). Additionally there are a few studies under way of immunotherapy with RT in the second line setting (NCT02701400, NCT03262454). Of note, in all of these trials RT has been targeted at thoracic lesions. To our knowledge, no trials with RT targeting metastatic lesions in combination with ICI have been previously done.

Stereotactic radiation therapy for liver metastases

Stereotactic radiation therapy for liver lesions has been well described for both primary hepatocellular carcinoma and metastatic disease³⁸⁻⁴⁰. In a large multi-institutional retrospective series of 427 patients with 568 liver metastatic lesions (from various histologies) treated with SBRT, local control (LC) of the treated lesions was durable. Median duration of local control was 51 months. Small tumors (< 40 cm³) were noted to have improved median local control rates of 52 months, compared to 39 months for tumor volumes \geq 40 cm³. No grade 3 or higher toxicity was reported. The selected dose/fractionation of 30 Gy in 3 fractions in the study has also been shown to be well tolerated⁴⁰. In a phase I dose-escalation study of SBRT for liver metastases, the 30 Gy in 3 fraction regimen shows no grade 3 or higher toxicity⁴¹. This regimen is also an accepted treatment dose for the current SABR-COMET-10 phase III trial analyzing the effect of ablative SBRT in patients with oligometastatic disease⁴².

